**Title: Functional Electrical Stimulation Use in Trans-tibial Amputations**

**Clinical Trials.gov ID: NCT02931396**

**Protocol Date: 4/15/2018**

## Background

Transcutaneous electrical stimulation (TENS) is an alternate form of electrical stimulation that historically used high frequencies for pain relief (1) but is now also administered at very low frequencies (sensory level TENS, 2-10 Hz) (2) TENS propagates along smaller afferent sensory fibers specifically to override pain impulses. When very low frequencies are used, TENS specifically targets sensory nerve fibers and does not activate motor fibers; therefore, no discernible muscle contraction is produced (3). Electrical stimulation is currently used in many forms to facilitate changes in muscle action and performance. In clinical settings, electrical stimulation can be used for improving muscle strength, increasing range of motion, reducing edema, decreasing atrophy, healing tissue, and decreasing pain. Neuromuscular electrical stimulation (NMES), used interchangeably with electrical stimulation (ES), is typically provided at higher frequencies (20-50 Hz) expressly to produce muscle tetany and contraction that can be used for "functional" purposes and can be found in literature as early as 1964 (4). This combination is known as functional electrical stimulation (FES). FES is applied to peripheral nerves that control specific muscles or muscle groups (5). Types of FES may activate musculature to restore lost abilities such as standing or grasping following neurological damage from CVA or SCI. FES may also assist with some secondary problems of neurologic damage such as poor circulation or slow wound healing (6). There is a paucity of studies evaluating the use and efficacy of FES to treat edema, skin integrity and residual limb, and chronic or phantom pain in individuals with TTA whereas FES research has been widely conducted with persons with other medical conditions such as Spinal Cord Injury (SCI), Multiple Sclerosis (MS), and Cerebrovascular Accident (CVA) (6,7,8).

Most studies on FES have shown positive results when combining FES with activity (e.g. knee flexion/extension exercises, cycling etc.) (9). It is difficult to exercise a muscle that has been amputated and is partially intact. FES conditions the muscle similar to exercise. Our clinical experience has found improvements in knee function, socket fit, and reductions in pain with wearing FES alone. With this study, one of the main functional outcomes that we are investigating is knee extension. We plan to place the FES electrodes on the medial and lateral quadriceps muscles in hope to show positive changes in muscle strength and volume. The gastroc/ soleus and tibialis anterior muscles have been amputated and have a secondary insertion point, therefore they are difficult to strengthen by exercising. We would like to investigate the effects of the FES on these two muscles in hopes to decrease atrophy or increase muscle volume. Should we demonstrate that FES alone helps improve the outcome measures in this study; it could potentially be a highly practical, easy to use, cost effective treatment that can be done at home.

**Objective:** To determine if at-home FES use without prosthetic wear results in benefits to persons with unilateral, trans-tibial amputations (TTA) who are at least two years status post their amputation surgery.

Hypothesis 1: FES will increase knee extension strength in the residual limb

Hypothesis 2: FES will increase volume of the residual limb

Hypothesis 3: FES will decrease chronic and phantom pain of the residual limb

Hypothesis 4: In comparison to the control group, FES training will show greater increases in velocity, step length, and percentage in stance time on the amputated limb after training when compared to baseline as measured using the GaitRite System.

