## Study Design and Methods

Subjects will be recruited and randomized into two groups using a random block method at the end of the baseline visit. One group will receive the FES intervention and the other group will continue with their activities of daily living. The study consists of a baseline visit and four follow up visits at 4 weeks, 8 weeks, 12 weeks and one final visit three months from the 12 week visit or from the discontinuation of the FES. Outcome measures will be taken for both groups during these visits. Each visit is expected to take no more than two hours.

Following informed consent, it will be verified and documented that participants meet the inclusion/exclusion criteria. Most of the inclusion/exclusion criteria are self report, with the exception of the monofilament evaluation and the evaluation of voluntary muscle contraction. An investigator will administer the tests. For the sensory testing the participant will be asked to close their eyes and inform the investigator when they sense the pressure of the monofilament on their LE. In order to continue with the study procedures, the participant must be able to feel a minimum of 7 of the 10 areas tested. Participants will also be evaluated to determine if a voluntary muscle contraction is present. To do this the FES electrode pads will be placed on the participant and the investigator must be able to observe a muscle contraction in order to proceed. Any participants who do not meet the inclusion/exclusion criteria for the study will be withdrawn.

The following procedures and outcome measures will be obtained from a blinded (second) assessor at the baseline visit.

1. Residual knee extension strength will be tested using a standardized Biodex protocol and a custom attachment (System 3, Biodex Medical Systems, NY). The participant will practice first on the biodex machine with their intact limb.

2. The residual limb volume will be measured with the use of a hand held three-dimensional motion-tracking laser scanner system. Reflective markers will be placed on a sock over the residual limb located at the tibial tubercle, fibular head, and anterior distal tibia. Circumferential measurements of the residual limb will be taken with a tape measure. Longitudinal measurements of the residual limb will be taken with a straight ruler. Using a standard scale, participant's height and weight will be recorded.

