Muscle performance will be evaluated at angular velocity of 60, during isokinetic quadriceps contractions. To assure familiarization with the procedures the participant will have two practice submaximal trial repetitions set at the velocity of 60 and one practice trial. The test will consist of 5 repetitions at 60/s. There will be a 60 second interval between repetitions tested. During evaluation, the participants will be verbally instructed to move the lever of the dynamometer as fast and as powerfully as possible, trying to produce a maximum torque. Any complaints reported by the participant will be recorded in the comment section and, if necessary, the test will be stopped. Using the same seat set up, muscle performance will be evaluated during static concentric (isometric) quadriceps extension contractions. The lever arm will be positioned at 60 degrees of knee flexion, with the support cushion modified for the amputee and positioned at mid calf. The participant will have one practice submaximal trial contraction. The test will consist of three contractions for five seconds each. There will be a 60 second interval between each test. During evaluation, the participants will be verbally instructed to move the lever of the dynamometer as powerfully as possible, trying to produce a maximum torque. Any complaints reported by the participant will be recorded in the comment section and, if necessary, the test will be stopped.

At the 12 week visit, the intervention group participants will return the FES device. They will be followed up with one final visit 3 months after the FES device is returned.

At the end of the study, should the study find the FES intervention is beneficial, we will offer the control group the same intervention. It will be optional per participant request.

If a subject misses the last visit or is dropped from the study for a reason not related to the study and or beyond our control, we will ask to set up a follow up visit, face to face, or a phone interview to allow us to gather end result information and complete the data analysis.

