## **Eligibility Criteria**

### **Inclusion Criteria:**

The inclusions include both men and women over the age of 18 years old. Participants are unilateral trans-tibial amputees with a minimum of a 4" residual limb. This length of amputation was chosen to provide for adequate surface area for the electrodes. The participants must be a minimum of one year postoperative to insure proper healing of the limb has occurred. The participants must have chronic limb pain and have had no prior experience in using TENS or FES. Participants must also demonstrate the ability to voluntary elicit a muscle contraction.

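### Hypotheses 1 to 3 name no comparator and the Statistical Plan names no deciding contrast, so a change shared by both arms could be read as an FES effect

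*Combined protocol and SAP*

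**What the plan says.** The hypotheses stand under the Objective, in the Background section. Three describe change under FES and name neither a comparator nor a time point:

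- The one on strength reads "Hypothesis 1: FES will increase knee extension strength in the residual limb".
- The one on limb size follows the same pattern, predicting a larger residual limb volume under FES.
- The one on pain reads "Hypothesis 3: FES will decrease chronic and phantom pain of the residual limb".

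The fourth is comparative: "In comparison to the control group, FES training will show greater increases in velocity", and it goes on to refer to step length, stance time and change from baseline.

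The design supports a comparison for every outcome. Study Design and Methods states: "Subjects will be recruited and randomized into two groups using a random block method at the end of the baseline visit". It also says that both groups are measured at the study visits.

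The Statistical Plan specifies a mixed model repeated measures ANOVA on the outcome measures, by group and over time, without limiting it to gait. Significant main and interaction effects at the 0.05 level lead to post-hoc comparisons over groups and visits, and no contrast is singled out. For non-normal data a general sentence promises nonparametric tests. The only one named for this purpose is Friedman.

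**The concern.** The contrast with Hypothesis 4 matters because the authors wrote out a control comparison where they wanted one. A reader may fairly take the other three as statements about change within the FES arm, and the Statistical Plan does not rule that out. A significant effect of time, or a baseline-to-follow-up change within the FES arm, is among the results that it invites. Neither separates FES from whatever else changes between visits.

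Strength is where a shared change is most plausible. The Biodex test is given at baseline and again at follow-up visits, after brief familiarisation of the residual limb: "the participant will have two practice submaximal trial repetitions set at the velocity of 60 and one practice trial". Some practice on the intact limb comes first. For pain, entry requires chronic limb pain ("The participants must have chronic limb pain and have had no prior experience in using TENS or FES"), but no score threshold is set, so how far scores would fall on retest is unknown. The documents suggest no mechanism for a spontaneous increase in volume.

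At stake is whether the randomised comparison decides three of the four hypotheses, including the one on knee extension, which the protocol calls a main functional outcome.

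**Working it through.** The documents give no sample size, power, effect size, SD or retest correlation, so there is no stated figure to reproduce. What follows illustrates how the answer depends on the choice of deciding test.

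**Assumed inputs.** No FES effect. The same shift *g* = 0.3 SD of the outcome in both arms from baseline to week 12. *n* = 15 per arm. Two-sided 0.05. Retest correlation ρ from 0.5 to 0.9.

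**Test A: paired test within the FES arm, not conditional on any other result.** The SD of the change, in outcome SD units, is √(2(1−ρ)). The standardised change is *d* = *g*/√(2(1−ρ)), and the non-centrality parameter is *d*√*n* with *n*−1 degrees of freedom.

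| ρ | *d* | *d*√15 | Rejects |
|---|---|---|---|
| 0.5 | 0.3/1.000 = 0.300 | 1.16 | 19% |
| 0.6 | 0.3/0.894 = 0.335 | 1.30 | 23% |
| 0.8 | 0.3/0.632 = 0.474 | 1.84 | 40% |
| 0.9 | 0.3/0.447 = 0.671 | 2.60 | 68% |

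At ρ = 0.8, other arm sizes give 27% (10), 52% (20) and 71% (30). At ρ = 0.8 and 15 per arm, shifts of 0.2 and 0.4 SD give 21% and 63%.

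**Test B: change over time with both arms combined.** With 30 participants and ρ = 0.8, the non-centrality parameter is 0.474 × √30 = 2.60, and a simple paired test rejects in 71%.

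**Test C: between-group difference in change.** The shift cancels: 0.3 − 0.3 = 0. The non-centrality parameter is zero and the rejection rate is the nominal 5%, whatever the shift, ρ or *n*. Simulation of a t-test on 12-week change gave 4% to 5%.

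**Friedman fallback.** Simulated over five visits, again with no FES effect. Here the shift is 0.2 to 0.5 SD of the *change score*, a different scale from *g*, with 10 to 30 per arm. Applied within the FES arm, Friedman rejects in 7% to 60% of trials; applied to both arms together, in 8% to 92%. Neither use compares the groups.

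The excess arises under A, B and Friedman and disappears under C. The plan does not say which of them decides.

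**The case against.** The strongest reply is that the control comparison is already planned. The trial is randomised, both groups are measured, and the mixed model covers all outcomes. A statement that FES increases strength is causal, and in a randomised trial it is ordinarily tested against control. Read strictly, the post-hoc sentence asks for main *and* interaction effects, and the interaction is the between-group difference in change. If the within-arm test were run only after a significant between-group difference, then under the same assumptions (ρ = 0.8) a finding in favour of FES would occur in about 2% of trials at 15 or 30 per arm, against 40% and 71% without that condition.

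Much of this stands. A reader might infer that the trial has no control comparison for strength, volume and pain, or that retest gains and regression of pain *would* be credited to FES. The documents support neither. No section says that a time effect or a within-arm change decides a hypothesis. Regression to the mean needs selection on a high value, which a requirement of chronic pain without a score threshold does not establish. The later offer of FES to controls is optional, depends on a finding of benefit, and is tied to no particular test.

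The reply leaves two gaps. The strict reading of the post-hoc sentence is one of several, since the text never says that the interaction comes first. And it does not reach the Friedman fallback, where the group comparison is lost on any reading.

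**Conclusion.** The point holds as an ambiguity that *could* credit non-FES change to FES, not as an error that the plan commits itself to. It rests on three features of the text: no comparator in Hypotheses 1 to 3, no deciding contrast in the Statistical Plan, and a named non-normal fallback without a group term.

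The 19% to 68% range depends on an assumed shift, an assumed arm size and an unconditional within-arm test, none of which the documents specify. It shows what the loose wording could cost and does not estimate this trial's error rate. The mechanism is credible for strength, uncertain for pain and unsupported for volume. Because the between-group analysis is already in the plan and only wording must change, this is a should-fix.

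**What to change.** 1. Reword Hypotheses 1 to 3 in the form of Hypothesis 4: compared with control, FES produces a greater increase in knee extension strength, a greater increase in residual limb volume, and a greater decrease in chronic and phantom pain, from baseline to week 12, the visit at which the device is returned.
2. State in the Statistical Plan that the group-by-time contrast, meaning the between-group difference in change from baseline to week 12, decides each hypothesis. Label time main effects and within-arm changes as supportive only.
3. Replace the Friedman test with a between-group method for non-normal data, such as a rank-based comparison of change scores.

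The cost is wording. No further data, visits or participants are needed. The price is that an improvement within the FES arm alone can no longer be claimed as an effect of FES.

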## Study Design and Methods

Subjects will be recruited and randomized into two groups using a random block method at the end of the baseline visit. One group will receive the FES intervention and the other group will continue with their activities of daily living. The study consists of a baseline visit and four follow up visits at 4 weeks, 8 weeks, 12 weeks and one final visit three months from the 12 week visit or from the discontinuation of the FES. Outcome measures will be taken for both groups during these visits. Each visit is expected to take no more than two hours.

Following informed consent, it will be verified and documented that participants meet the inclusion/exclusion criteria. Most of the inclusion/exclusion criteria are self report, with the exception of the monofilament evaluation and the evaluation of voluntary muscle contraction. An investigator will administer the tests. For the sensory testing the participant will be asked to close their eyes and inform the investigator when they sense the pressure of the monofilament on their LE. In order to continue with the study procedures, the participant must be able to feel a minimum of 7 of the 10 areas tested. Participants will also be evaluated to determine if a voluntary muscle contraction is present. To do this the FES electrode pads will be placed on the participant and the investigator must be able to observe a muscle contraction in order to proceed. Any participants who do not meet the inclusion/exclusion criteria for the study will be withdrawn.

The following procedures and outcome measures will be obtained from a blinded (second) assessor at the baseline visit.

1. Residual knee extension strength will be tested using a standardized Biodex protocol and a custom attachment (System 3, Biodex Medical Systems, NY). The participant will practice first on the biodex machine with their intact limb.

2. The residual limb volume will be measured with the use of a hand held three-dimensional motion-tracking laser scanner system. Reflective markers will be placed on a sock over the residual limb located at the tibial tubercle, fibular head, and anterior distal tibia. Circumferential measurements of the residual limb will be taken with a tape measure. Longitudinal measurements of the residual limb will be taken with a straight ruler. Using a standard scale, participant's height and weight will be recorded.

3. The participant will complete a pain questionnaire that addresses both chronic and residual limb pain.

4. The participant will fill out the Prosthetics Evaluation Questionnaire (PEQ). This survey measures outcomes in regards to prosthesis function and prosthesis related quality of life.

5. Participants will be tested with the GaitRite motion analysis system (<http://www.gaitrite.com/>). Participants will perform a 10 meter walk test in one direction at a self-selected walking speed. Participants will repeat this 3 times with brief rest periods in between as needed. Velocity, step length and percentage of stance time will be collected.

Study participants who are randomized into the intervention group will be fitted with a portable commercially available surface FES device. A trained investigator, [name], CPO, will fit the electrodes and explain the function of the FES device to the participant. The electrodes will be placed on the following locations: medial and lateral quadriceps, anterior tibialis (TA) and the gastrocnemius / soleus (GS) muscles on the residual limb. The FES settings will be individualized and optimized for eliciting muscle contraction of the residual limb while maintaining a comfortable level of stimulation. We will instruct participants on how to alternate the stimulation between the proximal knee (2 parts of the quadriceps) and the distal knee (TA and GS). Participants will be taught how to position the electrodes and how to operate the unit. They will be instructed to apply and wear the FES during a time of rest (non-active times of the day) and will be given extra sets of electrodes and batteries to use throughout the study. They will be provided with a pamphlet with simple instructions and photos on where and how to place, remove and store the electrodes. The instructions will include the wearing schedule and who to contact if they have questions.

We plan to use the recommended standard protocol settings in the product manual. We will start with the setting for the quadriceps muscles set at 300ms pulse width and 50Hz for the pulse rate. Channel 1 settings will be as follows: lag delay of 3 seconds, ramp up time of 3 seconds, on time of 12 seconds and ramp down of 2 seconds. Channel 2 settings will be as

follow: lag delay of 3 seconds, ramp up time of 2 seconds, on time of 9 seconds and ramp down of 1 second. For the smaller muscles of the gastroc/soleus and anterior tibialis muscles we will start with the setting of the 300ms pulse width and 35 Hz for the pulse rate. There will be no lag delay. Channel 1 settings will be as follows: ramp up time of 2 seconds, on time of 10 seconds and ramp down time of 2 seconds. Channel 2 settings will be as follows: ramp up time of 2 seconds, time on of 10 seconds and a ramp down for 2 seconds. The pulse rate and width will be increased at each visit per participant's comfort level.

We will record the settings at each visit and instruct the patient to not change the settings. The Continuum device locks the intensity increase buttons to prevent accidental increases in intensity. This safety feature is activated after 20 seconds of unchanged intensity.

Both study groups will be given daily logs to record daily prosthetic wearing times, changes in health, medications, activity, pain levels and FES use (the intervention group only).

Intervention group participants will be directed to use the FES for 15 contractions per muscle group (totally approximately 45 minutes) a minimum of three times per week for the next three months at home. We will set up a face-to-face visit with the FES participants at the end of the first week and call the FES participants every two weeks thereafter to check on compliance and address any issues with using the device. If the participant reports an ill-fitting prosthesis during the study, we will refer the participant to their local prosthetist for proper adjustments. If the prosthetic socket warrants replacement, the participant will be withdrawn from the FES intervention, we will perform the above mentioned outcome measures and continue to follow them until the 3 month final follow up visit.

At each follow up visit the log book entries will be collected and reviewed. A second investigator will inspect the residual limb and check the fit of the prosthetic socket, record residual limb knee extension strength on the Biodex machine, take anthropometric measurements (circumferences and lengths) of the residual limb with a tape measure and ruler, and scan the limb with the hand held three-dimensional motion-tracking laser scanner system. The participant will be asked to complete the pain questionnaire at all four followup visits and the Prosthetic Evaluation Questionnaire (PEQ) at the 12 weeks and 3 month followup visits.

For the isokinetic evaluation with the Biodex, the individuals will be positioned in the dynamometer, sitting with the trunk, pelvis and thigh stabilized by belts. The back of the chair will be inclined at an 85 degree angle and the rotational axis of the device will be aligned with the rotational axis of the knee joint, at the level of the lateral epicondyle of the femur. The lever arm was positioned parallel to the leg, with the support cushion modified for the amputee and positioned at the mid-calf. The test will be performed in a total range of motion of 110 degrees. The knees will be positioned in 60 degrees of flexion to start.

Muscle performance will be evaluated at angular velocity of 60, during isokinetic quadriceps contractions. To assure familiarization with the procedures the participant will have two practice submaximal trial repetitions set at the velocity of 60 and one practice trial. The test will consist of 5 repetitions at 60/s. There will be a 60 second interval between repetitions tested. During evaluation, the participants will be verbally instructed to move the lever of the dynamometer as fast and as powerfully as possible, trying to produce a maximum torque. Any complaints reported by the participant will be recorded in the comment section and, if necessary, the test will be stopped. Using the same seat set up, muscle performance will be evaluated during static concentric (isometric) quadriceps extension contractions. The lever arm will be positioned at 60 degrees of knee flexion, with the support cushion modified for the amputee and positioned at mid calf. The participant will have one practice submaximal trial contraction. The test will consist of three contractions for five seconds each. There will be a 60 second interval between each test. During evaluation, the participants will be verbally instructed to move the lever of the dynamometer as powerfully as possible, trying to produce a maximum torque. Any complaints reported by the participant will be recorded in the comment section and, if necessary, the test will be stopped.

At the 12 week visit, the intervention group participants will return the FES device. They will be followed up with one final visit 3 months after the FES device is returned.

At the end of the study, should the study find the FES intervention is beneficial, we will offer the control group the same intervention. It will be optional per participant request.

If a subject misses the last visit or is dropped from the study for a reason not related to the study and or beyond our control, we will ask to set up a follow up visit, face to face, or a phone interview to allow us to gather end result information and complete the data analysis.

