### **Exclusion Criteria:**

The exclusion criteria include having a cardiac condition, such as hypertension, congestive heart failure, etc. The exclusions will be subjects who have a pacemaker and have impaired sensation measured by a monofilament test (unable to feel a minimum of 7/10 areas tested). The use of FES may interfere with a pacemaker and is not suggested for people who have a pacemaker. People with insensate skin and or neuropathy may lead to inappropriate threshold tolerance to the FES. Also, participants with a BMI greater than 42 kg/m^2 will be excluded as the FES does not work effectively with excessive adipose tissue.

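### The 7-of-10 monofilament rule is not tied to the residual limb or to the four electrode sites, so a participant can pass with up to three electrode sites insensate, or with sites untested

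*Combined protocol and SAP*

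**What the plan says.** Study Design and Methods describes two hands-on eligibility checks after consent. In the sensory check the participant, eyes closed, is to "inform the investigator when they sense the pressure of the monofilament on their LE". To continue, "the participant must be able to feel a minimum of 7 of the 10 areas tested". In the second check the electrode pads are put on and "the investigator must be able to observe a muscle contraction in order to proceed".

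The Exclusion Criteria restate the sensory rule as "impaired sensation measured by a monofilament test (unable to feel a minimum of 7/10 areas tested" and give its reason: "People with insensate skin and or neuropathy may lead to inappropriate threshold tolerance to the FES".

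The electrodes go on the "medial and lateral quadriceps, anterior tibialis (TA) and the gastrocnemius / soleus (GS) muscles on the residual limb". Settings are to be "optimized for eliciting muscle contraction of the residual limb while maintaining a comfortable level of stimulation", and the same section has pulse rate and width stepped up at each visit according to comfort. The device is then used at home for three months.

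Participants are "randomized into two groups using a random block method at the end of the baseline visit", so eligibility checks made at that visit can be completed before allocation.

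**The concern.** The reason given for the criterion is local: what matters is whether the skin under a pad can feel. The rule is global: it counts areas felt, wherever they lie. Participants are unilateral amputees, and the text does not say which lower limb is tested, which ten areas are used, or whether any of them is an electrode site.

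Comfort is one of the two stated guides when settings are first chosen (contraction is the other), and it governs the later increases. It is a weaker guide where skin has no feeling, which is the hazard the Exclusion Criteria name. At stake is the safety of FES participants, and of any controls who later take up the intervention that the protocol offers them if it proves beneficial.

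**Working it through.** The documents give no figure to reproduce, so the check is a count.

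**Inputs.** Areas tested: 10. Minimum felt to pass: 7 (Study Design and Methods; Exclusion Criteria). Electrode sites: 4, all on the residual limb (Study Design and Methods). Number of electrode sites among the 10 areas: not stated; call it m and let it run from 0 to 4. Assumption: one test area per electrode site.

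**Formulas.** A pass permits at most 10 − 7 = 3 areas not felt. For a participant who passes:

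- sites that may have failed = min(3, m)
- sites untested = 4 − m
- sites assured to be felt = max(0, m − 3)

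| m | may have failed | untested | assured felt |
|---|---|---|---|
| 0 | 0 | 4 | 0 |
| 1 | 1 | 3 | 0 |
| 2 | 2 | 2 | 0 |
| 3 | 3 | 1 | 0 |
| 4 | 3 | 0 | 1 |

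Testing the intact limb would correspond to m = 0. Testing the residual limb settles the side but leaves m anywhere from 0 to 4, and even m = 4 assures only one site.

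**Sensitivity to the assumption.** If each site carried two test areas (8 of the 10), three failures could cover one site completely and half of another (3 = 2 + 1). The count of sites is smaller, but sensation at every site is still not assured.

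**With the proposed rule.** m = 4 and each site must be felt: 0 failed, 0 untested, 4 assured. Up to three of the other 10 − 4 = 6 areas may still fail under the overall count.

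**Do other provisions close the gap?**

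- Contraction check at screening: its criterion is a motor response, not skin sensation.
- Fitting by a trained investigator, starting from the product manual's settings: gives some sensory feedback through comfort, but has no pass/fail threshold.
- Instruction not to change settings, and the intensity lock: guard against changes at home, not against a level set too high at the visit.
- Week-1 visit, two-weekly calls and daily logs: allow problems to be reported, largely by what the participant notices.
- Limb inspection at follow-up: can find skin harm after it has occurred.

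Each helps. None is a sensory criterion at the electrode sites.

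**The case against.** The case on the other side has four parts.

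1. **The side can be inferred.** The rationale concerns tolerance of FES, and every electrode is on the residual limb, so a sensible investigator would test that limb. This is fair. On its own the unnamed side is a missing detail, and a reader who inferred that the intact limb is tested would go beyond the text. The count rule remains open even on the residual limb.

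2. **A count is a reasonable neuropathy screen.** The rationale mentions neuropathy as well as insensate skin, and ten areas serve the former. That is a reason to keep 7 of 10. It does not cover the other half of the stated purpose.

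3. **Fitting gives sensory feedback.** Settings are found with the participant's response at the treated sites and an investigator present, and increases are made at visits. Absent feeling could surface there. This stands as mitigation, so it would be wrong to say that nothing in the plan bears on sensation under the pads. It is not a formal check.

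4. **The table is a worst case, not a risk.** This also stands. A reader might infer that participants will be stimulated on insensate skin, or that untested skin should be counted as insensate. The documents support neither: m is unknown, untested skin may feel normally, and nothing indicates how often a passing participant would have a failed electrode site.

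**Conclusion.** The point holds as a participant-safety gap in the eligibility rule. Followed exactly, the criterion can admit someone with up to three of four electrode sites insensate (m = 3 or 4), or with one to four sites untested (m = 3 down to 0). This rests on one test area per site. The broader conclusion, that a pass does not assure sensation at all four sites, also held with two areas per site.

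The gap is clear from the text, but its frequency is not, and the existing safeguards reduce the risk. The change should be made because the rule does not secure its own stated purpose and the remedy is inexpensive. No endpoint, sample size or analysis is affected.

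**What to change.** In Study Design and Methods and in the Exclusion Criteria, state that:

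- the monofilament test is done on the amputated limb;
- the 10 areas include the skin at the four planned electrode sites (medial quadriceps, lateral quadriceps, tibialis anterior, gastrocnemius/soleus);
- in addition to 7 of 10 overall, each electrode site must be felt;
- the rule applies to all candidates before randomization, so both groups are selected alike, and the result is recorded by site.

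Small repositioning over the same muscle may be left to the fitting investigator's discretion, provided the new site is felt. Room for this may be limited below the knee, since the Inclusion Criteria admit residual limbs as short as 4 inches, so it should be an allowance rather than a required procedure.

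**Cost.** The test, investigator and visit stay the same. The wording changes in two places and the screening record gains a by-site entry. Some test areas may have to change, and there may be a few more screen failures, a number the documents do not allow us to estimate. Any repositioning adds a retest and departs from the standard electrode placement shown in the participant's pamphlet.
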